Potential participants will be directed to a website that will include a brief description of the study and a link to a short, online eligibility screener. Participants will be asked to consent to an eligibility screener. This will allow us to retain all data from these screeners and compare/contrast who sought to enroll in the trial. For the purpose of this study, "eligible" participants will have access to the intervention modules. Ineligible participants will be thanked for their time and redirected to the Google homepage. Eligible participants will then be asked to complete a study consent form. Consistent with prior studies with youth, we have designed our consent form so that participants have to consent to the different elements of the consent process. This strategy reduces the likelihood that prospective participants will scroll down and not take a moment to examine their rights as participants and the study procedures. The consent outlines the voluntary nature of the study, participant's freedom to discontinue the survey at any time, approval to retain data for future research, approval to retain email addresses to send incentives, and the procedures to guarantee their confidentiality.

Finally, we recognize that consent is an ongoing process. Participants will have access to the consent form at all times, as a copy is programmed to be available in the menu of the application. Participants in

the Intervention arm will be assented at each Peer Mentor session and made sure that they want to have their scheduled session. If a participant wishes to dis-enroll from the study, they can do so by deactivating their account in the WebApp's Profile menu or reaching the MPIs via phone or email

2. Waiver of Informed Consent:

No Waiver Requested

RESOURCES NECESSARY FOR HUMAN RESEARCH PROTECTION:

As noted in the protocol, our team is comprised by an interdisciplinary team of psychologists and public health professionals with expertise in conducting research with youth, sexual and gender minorities, and racial/ethnic minorities through technology-assisted interventions. All staff will complete human subjects research training and data safety training as part of their project on-boarding. We have both the physical and virtual infrastructure necessary to carry out this project and ensure the protection of human subjects. All study staff who are expected to interact with study participants will be expected to complete a training in Mental Health First Aid. Youth Navigators will also be trained in motivational interviewing skills and crisis identification. They will be required to demonstrate proficiency in these techniques before they can interact with participants. Along with on-going supervision, we have also scheduled weekly supervision meetings to reinforce protocol guidelines and strengthen their skills. In-person data collection will occur at the [name] Psychiatry offices. Participants will complete the surveys in one of our private therapy offices on the 6th floor. We have locked filing cabinets to keep any paper records, but the default will be to use RedCap for data entry.

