any questions on the surveys that they are uncomfortable answering. They will also be informed about the limits of confidentiality as it relates to imminent suicide risk or risk of imminent harm to others and the need to enact emergency procedures to ensure their safety and the safety of others. Psychological distress is a potential risk to EASM during the completion of the interviews or surveys, reading the intervention content, creating a safety plan at the baseline evaluation, and during the peer mentor session. We will provide EASM with information to allow them to contact the study team at any time if they experience psychological distress related to participation in the study. In addition, at the time of study enrollment, we will solicit up to 3 personal contacts of study participants to call in the event that a participant is in a psychiatric crisis but is unreachable for some reason. We will inform participants about why we are collecting information for these emergency contacts, remind them that providing this information is optional, and describe to them the procedure for calling these contacts in the event of an emergency. We will clarify with participants what information will and will not be shared with the emergency contacts. For instance, we will share that we are calling from the Penn Health System and are worried about the participant and want to make sure that he is okay but are unable to reach him. We will then ask the emergency contact whether they have been in touch with the participant and could help us to locate him. We will not reveal the name of the research study or provide any information that has the capacity to unintentionally reveal the sexual or gender orientation of the participant. We will share with participants that they have permission to revoke consent for us to contact these emergency contacts at any time, and to just let us know that preference verbally or in writing. [name] has used this strategy successfully for working with individuals who are living with HIV and who reported past month suicidal ideation. In the prior studies that used this approach, most participants provided at least one study contact, though we never needed to call any of the emergency contacts because of the strong rapport that we established with participants during the baseline assessment and other research procedures. If psychological distress is apparent during a peer mentor session or other study contact, our licensed clinicians will be available to talk with the participant. Our licensed clinicians are familiar with the emergency management protocols at Penn and throughout the city of Philadelphia. If needed, we will participants in immediate crisis to the Mobile Crisis Response Team which is available 24 hours a day, 7 days a week. This Mobile Crisis Team is a service offered through the city of Philadelphia that can drive to patients/participants home to help transport them to the psychiatric emergency department, or can de-escalate the risk at home. In addition, participants will be provided with the number for the National Suicide Prevention Lifeline and the licensed study clinician at the time of consent. Some participants may opt to include the number for the Mobile Crisis Response Team, the National Suicide Prevention Lifeline, or the number of the licensed study clinician to their Safety Plan, but this will not be required. Research staff will receive training in crisis assessment and management procedures to assist with the management of suicidal and/or homicidal ideation, or child physical/sexual abuse. We will notify participants when we must engage in mandatory reporting during the consent process and when the participant decides to share a reportable event with study staff. At the beginning of any phone contact with participants, the researcher will first ask the participant to identify their physical location. This will ensure that if deployment of emergency services is required, we know how to reach the participant in crisis. Unintended disclosure is also a potential risk. Participants will be instructed at different moments during the study (e.g., screening, baseline, follow-up) of steps they can take to further protect their privacy (e.g., clear browser history; avoid saving username/password in browser; logging out every time; using the app in private; using a screen lock on their phones, if parents allow).

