MI based peer-to-peer sessions are provided using HIPAA compliant virtual platform (BlueJeans, Zoom). Participants will have the option to use the virtual platform in several formats: face-to-face video chat, video chat in which they can see the PM but the PM cannot see them, audio chat only, or a text based conversation. The consent form will include a full description of their options, and will also make it clear that they can opt to have as many or few virtual sessions they wish (after the introductory session).

Participants will request a peer mentors session through the STARS App: when requesting a virtual session participants will be able to indicate the format they would like the session to take (e.g., face to face or audio only). Zoom is compatible on PCs, tablets and smartphones. One potential challenge is the security and confidentiality of virtual platforms. Zooms is HIPAA-compliant as access through <https://pennmedicine.zoom.us/> Only the introductory virtual session is mandatory: after this, participants can opt to have as many sessions as they wish.

Each of the PM will be trained in Motivational Interviewing (MI) and supervised by a trained counselor during these sessions. Motivational interventions are collaborative and non-confrontational and engagement strategies combined with employing the MI spirit eschew any form of coercion or threat, as one of the key principles of MI is autonomy support.

Given the nature of the participants in the study, staff will receive training in crisis assessment and

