management procedures to handle both suicidal crises, as well as reports of homicidal ideation and risk of child abuse. We will use established protocols from our prior studies conducted with men who have sex with men (MSM) and with individuals at high risk for suicide to guide research staff in responding to crisis or harm situations, including attempting to contact the participant to assess risk level and provide appropriate follow-up (e.g., crisis hotline, safety check, suicide hotline). Staff will be required to contact our full-time clinical counselor ([name]) or clinician ([name]) to manage situations of higher risk. Risk of coercion. Using online recruitment methods where the intervention is not pitched by a recruiter minimizes the risk of potential coercion. Instead, EASM will be able to choose and click on the recruitment advertisement and decide if they wish to learn more or not. Similarly, staff will be trained to discuss all elements of the consent process with potential participants. Consent documents will fully explain the study procedures, potential risks, and potential benefits. Participants will also be reminded that the study participation is voluntary and that refusing to participate in the study or withdrawing from the study is an option at any time. Informed consent documents will be available in English and have grade 5 reading level. Adequacy of Protection against Risks a. Recruitment and Informed Consent We will recruit subjects through the placement of banner advertisements on Facebook and other social media outlets. For those who click on the ad, they will be taken to a page describing the nature of the study: if they then click on interested in participating they will be asked to complete an interest form which will be used by study staff to schedule an in-person visit. During the in-person visit, eligible participants will be given a written informed consent document. We will employ several strategies to offset risks of loss of confidentiality related to participating in our trial. First, we will petition a Certificate of Confidentiality from the Department of Health and Human Services (an explanation will follow indicating that in studies thus covered the researchers have not been forced to release any research data from participants, even under a court order or subpoena). Participants who experience distress during the survey can access our list of community referrals, which can be viewed on our study's application, or contact the research team directly (toll-free number is embedded into the About Us section of the application). Participants can contact study staff to get referrals to local services, and should participants report or display signs of distress during the teleconference interactions they will be asked to speak with a clinician who is a member of the research team. Any unexpected adverse events will be immediately reported to the IRB, and all study activities will halt pending IRB review and recommendations. It will be made clear to all participants in the consent forms that participation in the pilot RCT will not affect their access to any services in their community. The consent document will make it clear that participants can attend any services in their local area and that they do not have to participate in the trial to access services, nor do they have to reveal their participation in the trial to anyone at these agencies. Participants who chose not to participate in the trial will still be able to access the list of local LGBT resources. Participants addresses and any other identifying information will be kept in a separate, password-protected file to avoid risk of identification. All stored data will be kept in a locked room at the University of Pennsylvania. Electronic data will be maintained in a secure server. Access to the data will be located in a folder with restrictions (i.e., may be accessed only by study team members). Access to data will be on a role-based standard; only those study staff that require access to identifying data to complete their study-related roles will be allowed access, as described above. All study staff will be trained in security and confidentiality procedures, and will sign a confidentiality agreement before receiving access to any participant data. We will also develop procedures to minimize indirect disclosure that a participant is enrolled in a study focused on EASMs suicide vulnerability. For each mode of re-contact information,

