
we will ask specifically whether anyone else potentially has access to that mode of communication, and if it is acceptable to leave a non-specific message about participation in a health study. The contact information and permissions will be updated quarterly. No study-related messages will ever mention the nature of the research study. Additionally, all scripts for email, text message, and telephone contact with participants will be reviewed and approved by the University of Pennsylvania IRB before being used for contact with participants. Participants confidentiality will be breached only to protect the safety and welfare of research participants and only in accordance with state and federal law. The exceptions to confidentiality include if the participant reports imminent suicide risk, homicidality, or the physical or sexual abuse of a child. If necessary, authorities will be notified. Although study assessments will not ask about these issues, in the unlikely event that a participant self-discloses this information to study staff, during virtual tele-conference sessions, or through open fields (e.g., additional comments) in the surveys, we will activate our Adverse Events Reporting protocol (see below). These exceptions to breaking confidentiality the case where a participant reveals child abuse, imminent suicide risk, or homicidality will be explained in detail to participants and prior to completing the consent process.

b. Protections against Risk

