data. Because this is a WebApp, participants are able to access the content and resource guide at a location of their choice on a computer, phone, or tablet. When a participant accesses the study website, content is transmitted securely using the Transport Layer Security (TLS) protocol, the same protocol used to protect financial and other personal information when transmitted from a web site to a user's browser. This prevents anyone else on the network from intercepting and viewing the content that is being provided by or to the participant. Additionally, if a participant opts-in to receiving text message reminders, they will need to log in to the survey with their username and password. That way, if someone picks up the participant's phone, they will not be able to access the participant's survey account. Data are provided to researchers in de-identified form, with all personally identifying information removed. Data that are provided to researchers is encrypted if it is transmitted across the Internet. At the end of the research study, all data are permanently de-identified for archive and distribution to other researchers.

4. Subject Confidentiality:

How will confidentiality of data be maintained? Check all that apply.

- Paper-based records will be kept in a secure location and only be accessible to personnel involved in the study.
- Computer-based files will only be made available to personnel involved in the study through the use of access privileges and passwords.
- Prior to access to any study-related information, personnel will be required to sign statements agreeing to protect the security and confidentiality of identifiable information.
- Whenever feasible, identifiers will be removed from study-related information.
- A Certificate of Confidentiality will be obtained, because the research could place the subject at risk of criminal or civil liability or cause damage to the subject's financial standing, employability, or liability.
- A waiver of documentation of consent is being requested, because the only link between the subject and the study would be the consent document and the primary risk is a breach of confidentiality. (This is not an option for FDA-regulated research.)
- Precautions are in place to ensure the data is secure by using passwords and encryption, because the research involves web-based surveys.
- Audio and/or video recordings will be transcribed and then destroyed to eliminate audible identification of subjects.

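### The location question that lets staff send emergency help is stated for phone contact but not for the virtual peer-mentor sessions

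*Combined protocol and SAP*

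**What the plan says.** All places are in the combined protocol and SAP.

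- **The rule.** Risk/Benefit Assessment, 1. Risks: "At the beginning of any phone contact with participants, the researcher will first ask the participant to identify their physical location". The reason follows directly: "This will ensure that if deployment of emergency services is required, we know how to reach the participant in crisis".
- **The sessions.** The same section puts peer-mentor sessions on a virtual platform (BlueJeans, Zoom). Besides face-to-face video, participants may choose "video chat in which they can see the PM but the PM cannot see them, audio chat only, or a text based conversation". On number: "Only the introductory virtual session is mandatory"; further sessions are at the participant's option.
- **Foreseen trouble.** The Risks section includes among the occasions for psychological distress "creating a safety plan at the baseline evaluation, and during the peer mentor session". Under Adequacy of Protection against Risks, a. Recruitment and Informed Consent, the plan adds: "should participants report or display signs of distress during the teleconference interactions they will be asked to speak with a clinician". When it describes the exceptions to confidentiality (imminent suicide risk, homicidality, child abuse), it provides for adverse-event reporting "in the unlikely event that a participant self-discloses this information to study staff, during virtual tele-conference sessions".
- **Assent.** Informed Consent, 1. Consent Process, has intervention-arm participants assented at every peer-mentor session.

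**The concern.** Everyone in this trial reported suicidal ideation in the month before entry. The sponsor judged that in a phone call staff should know at the outset where the person is, because a crisis may require sending someone. A peer-mentor session is also a live remote contact, and the plan itself names it as a place where distress or imminent risk may come to light. As written, the session can begin and end without anyone asking where the participant is.

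What is at stake is patient safety in one arm. Suppose a STARS participant discloses imminent risk and then drops the connection. Staff can call back, and the phone rule then applies if the call is answered. If it is not, they must work from the address on file and from other people's knowledge. Nothing here touches the estimates of treatment effect.

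**Working it through.** No arithmetic decides this point, and the plan gives no figure to reproduce. The check sets the rule beside the sessions, then asks what each stated safeguard supplies.

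**1. Does the phone rule already reach the sessions?** Three features say it does not.
- *Mode.* Under Methods, 7. Subject Follow-up, the word phone is used for the clinical interviews at 2, 4 and 6 months. Mentor sessions are described as virtual or teleconference contacts, usable on PCs, tablets and smartphones. A text chat or a one-way video on a PC is not a phone contact.
- *Who asks.* The rule assigns the question to the researcher. A peer mentor leads the session.
- *Any other rule.* The session description, the distress and disclosure text, the consent process and the staff-training text (Resources Necessary for Human Research Protection) contain no location step. The phone rule is the only one in the document.

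**2. Can the location be seen instead?** There are four formats. In three of them (one-way video, audio, text) the mentor does not see the participant. Even two-way video shows surroundings, not an address.

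**3. What does each stated safeguard supply if the participant disconnects?**

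| Safeguard | Where stated | What it supplies | Current location recorded beforehand? |
|---|---|---|---|
| Counselor supervises sessions | Risks | A trained person to recognise the crisis | No |
| Hand-off to a clinician | Risks; Recruitment and Informed Consent | Clinical assessment, while the participant stays in contact | No |
| Attempted re-contact, safety check | Risks | A call-back, where the phone rule applies if answered; a check | No |
| Up to three emergency contacts, optional and revocable | Risks | People who may help find an unreachable participant | No |
| City Mobile Crisis Response Team, 24 hours a day | Risks | A team that can travel to the home | No; it needs a place to go |
| Street address | 5. Protected Health Information | An address on file | No; it may or may not be where they are |

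Each row lowers the risk. No row does what the phone rule does, which is to record the present location before it is needed.

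**4. Exposure.** STARS has 32 planned participants and one mandatory session each: 32 × 1 = 32 planned introductory sessions. The number of optional sessions is not given, nor is any rate of disclosure or disconnection. This counts contacts without the stated step. It does not measure risk.

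**The case against.** The strongest reply is that the scenario is largely handled. Emergency contacts are collected for exactly the participant who is in crisis and cannot be reached, and staff would ask them to help locate that person. The Risks section reports that in prior studies most participants gave at least one contact and none ever had to be called. The crisis team can go to the home, which gives the address on file a practical use. Everyone completes a Safety Planning Intervention with a licensed clinician before randomization. Staff who deal with participants train in Mental Health First Aid, and Youth Navigators must show proficiency in crisis identification. All this stands and lowers the weight of the point. What remains is that contacts are optional, revocable and slower than a question already answered.

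A second reply is that the gap may be one of drafting. The phone sentence sits in the same block of crisis text as the mention of distress in a mentor session, and an audio session may run on a smartphone. The prior-study crisis protocols are relied on but not reproduced. The looser reading of phone is weak, given the text and PC formats and the named researcher. The unseen protocols are a fair reservation: the step may exist there.

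A third reply is that the two kinds of contact differ in risk. The repeated suicide-severity measure is interview-rated and the follow-up clinical interviews are by phone, so those calls probably ask about suicidal thoughts by design. Mentor sessions are supervised, and the plan calls disclosure there unlikely. This also stands: the reason for the phone rule carries over, but not with equal force.

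**Conclusion.** The point holds in a limited form. The plan states a location check for phone contact and none for the virtual peer-mentor sessions, although it foresees distress and disclosure of imminent risk in them. The stated safeguards mitigate the gap but do not record current location before a disconnection. It is a worthwhile, inexpensive safety improvement for the STARS arm, not a failure of the crisis plan. It rests on reading phone contact in its ordinary sense and on the protocol text alone.

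A reader might infer more, and the documents do not support it:
- *That staff could not find a participant who disconnects.* The emergency-contact procedure, safety check, crisis team and address all bear on that.
- *That the study has no such step at all.* The prior-study protocols are not reproduced, so only its absence from this plan can be asserted.
- *That participants are known to take sessions away from home.* The Subject Privacy text, "participants are able to access the content and resource guide at a location of their choice on a computer, phone, or tablet", concerns app content, not live sessions. Being elsewhere is plausible, but the plan does not say so.
- *That a share of contacts lacking the step expresses the danger.* Such a ratio depends on which contacts are counted, omits optional sessions and other calls of unknown number, and measures no risk.

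**What to change.** In Risk/Benefit Assessment, 1. Risks, replace any phone contact with: any live remote contact, including every virtual peer-mentor session in any format. State that in mentor sessions the peer mentor or the supervising counselor asks, at the assent already taken at each session. If the prior-study crisis protocols already contain the step, a citation in the description of the virtual sessions is enough.

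The cost is one extra question per session and slight discomfort for participants who chose a camera-off or text format for privacy. A short explanation that the answer is for emergency use should ease that. No change to the design, outcomes or analysis is needed.
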